endpoint are based on the sample size that was initially driven by the Worst Pain CFB endpoint as described above. With a 2-sided significance level of 0.025, the sample size of 104:52 in the subset of participants reporting Baseline HSSDD worst skin pain score at or beyond the threshold for clinically meaningful change (ie, Baseline HSSDD ≥ 3) provides 53% power for detecting a statistically significant difference between bimekizumab [REDACTED] and placebo in the proportion of Worst Pain responders.

Note that the power at the 0.025 level of significance associated with this endpoint for the comparison between bimekizumab [REDACTED] and placebo is 95%. The [REDACTED] comparison of Worst Skin Pain response vs placebo against the 0.05 level of significance is therefore likely, and the power at this significance level is 65%. Given the strength of the power for the bimekizumab [REDACTED] arm vs placebo across endpoints, it is considered acceptable to have a relatively low power for this final endpoint in the testing sequence for the bimekizumab [REDACTED] treatment arm vs placebo.

Table 2–1: Power calculation assumptions and methods

Endpoint	Power $\alpha = 0.025$, 2-sided		Assumptions		
	[REDACTED]	[REDACTED]	Week 16 Bimekizumab [REDACTED] N=280 ^a	Week 16 Bimekizumab [REDACTED] N=140	Week 16 Placebo N=70
HiSCR ₅₀	0.99	0.90	Proportion responders=0.60	Proportion responders=0.50	Proportion responders=0.25
HiSCR ₇₅	0.99	0.98	Proportion responders=0.45	Proportion responders=0.35	Proportion responders=0.10
Flare	0.99	0.99	Proportion of participants with flare by Week 16=0.09	Proportion of participants with flare by Week 16=0.19	Proportion of participants with flare by Week 16=0.52
DLQI	0.99	0.96	Mean CFB=-5.4; SD=6.8	Mean CFB=-4.8; SD=6.8	Mean CFB=-0.8; SD=6.6
Worst Skin Pain CFB ^b	0.89	0.73	Mean CFB=-2.2; SD=3.2	Mean CFB=-2.0; SD=3.2	Mean CFB=-0.5; SD=3.7
Worst Skin Pain Response ^c	0.95	0.53	Proportion responders=0.53	Proportion responders=0.43	Proportion responders=0.23

CFB=change from Baseline; [REDACTED] SD=standard deviation

Note: Estimates for HS0004 are based on Week 12 data from the HS0001 study.

^a Pooled [REDACTED] at Week 16 from [REDACTED] and [REDACTED] arms

^b Within-participant average of Worst Skin Pain according to 24-hour recall.

^c Assumes N=208, 104, 52 in [REDACTED] and placebo, respectively, to account for Worst Skin Pain score at or above 3 (ie, the threshold for clinically meaningful change from Baseline)

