4 STATISTICAL/ANALYTICAL ISSUES

4.1 Adjustments for covariates

The primary efficacy analyses and selected secondary analyses will be adjusted for the 2 randomization stratification variables:

- Hurley Stage at Baseline (II or III)
- Baseline antibiotic use (Yes or No)

If a participant is stratified in the incorrect stratum (ie, the stratum recorded in the Interactive voice or web Response System differs from the actual stratum the participant belongs to), the actual stratum will be used for the analysis.

The continuous secondary endpoints will also include the Baseline value as a covariate.

The Worst Skin Pain secondary endpoints (change from Baseline continuous endpoint and pain response binary endpoint) will also include analgesic use as a covariate.

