Change from Baseline in worst skin pain score will be presented by treatment group. The analysis model will be based on an ANCOVA with fixed effects of treatment, Hurley Stage at Baseline, Baseline antibiotic use, analgesic use (Section 6.4.2) and Baseline value as a covariate.

The LSM, SE, and 95% CI for the LSM will be presented by treatment group. For the comparison between placebo and bimekizumab, the difference between the LSM, the associated 97.5% CI for the contrasts, and the corresponding p-value will be presented. If one dose regimen is tested at the 0.05 significance level as determined in Section 4.5, then the confidence interval will be 95% instead of 97.5% for that dose with a corresponding $Z_{\alpha/2}$ of 1.96.

8.3.4.2 Sensitivity analysis of change from Baseline in skin pain score at Week 16

A sensitivity analysis using the same analysis model as in Section 8.3.4.1 will be used, based on observed data. Estimand and intercurrent event details are specified in Table 8–2.

8.3.5 HSSDD skin pain response at Week 16

The analysis set for the analyses of the skin pain response will be restricted to those study participants in the RS with a Baseline worst skin pain score of 3 or higher. The weekly scores and Baseline score are derived as specified in Section 8.3.4.

8.3.5.1 Primary analysis of skin pain response at Week 16

Skin pain response at Week 16, as assessed by the “worst skin pain” item in the HSSDD, is defined as an improvement in the weekly worst skin pain score of at least 3 points versus Baseline.

The primary analysis will be based on a logistic regression model including a fixed effect for treatment, Hurley stage at Baseline, Baseline antibiotic use, and analgesic use (Section 6.4.2).

The odds ratio versus placebo, p-value (from Wald test), and 97.5% CI will be calculated. If one dose regimen is tested at the 0.05 significance level as determined in Section 4.5, then the confidence interval will be 95% instead of 97.5% for that dose. Missing data will be handled as specified in Section 4.2.1.2. Estimand and intercurrent event details are specified in Table 8–2.

The number and percentage of participants who are pain responders at Week 16 will be summarized by treatment group.

By-participant listings of pain response status will be provided.

8.3.5.2 Sensitivity analyses of Skin Pain Response at Week 16

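### The skin pain response model leaves out the Baseline pain score; adding it would keep or raise power at almost no cost

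*SAP*

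**What the plan says.** Section 8.3.5 limits the analysis to participants "restricted to those study participants in the RS with a Baseline worst skin pain score of 3 or higher". Section 8.3.5.1 defines response as "an improvement in the weekly worst skin pain score of at least 3 points versus Baseline" and fits a "logistic regression model including a fixed effect for treatment, Hurley stage at Baseline, Baseline antibiotic use, and analgesic use (Section 6.4.2"). The nonresponse-imputation and observed-case analyses (8.3.5.2.1 and 8.3.5.2.2) reuse that model.

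For the change score of the same diary item, Section 8.3.4.1 specifies an ANCOVA whose terms include "analgesic use (Section 6.4.2) and Baseline value as a covariate".

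Section 4.1 sets the general rule behind both models: "The continuous secondary endpoints will also include the Baseline value as a covariate". For the pain endpoints it adds one thing: "The Worst Skin Pain secondary endpoints (change from Baseline continuous endpoint and pain response binary endpoint) will also include analgesic use as a covariate".

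On power, Section 2.4 states: "With a 2-sided significance level of 0.025, the sample size of 104:52 in the subset" with Baseline pain of 3 or more "provides 53% power for detecting a statistically significant difference between bimekizumab" and placebo. It gives 65% at 0.05 for the same comparison and 95% at 0.025 for the other dose. It then says that relatively low power is acceptable for the single-arm dose on this last endpoint.

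The dose names are blacked out. Below, the single-arm dose is the one given in one arm up to Week 16 (N=140). The pooled dose is the one combined across two arms (N=280).

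**The concern.** Response is a fixed 3-point fall on a 0 to 10 scale. A participant who starts at 3 must have a weekly average of 0 at Week 16, while one who starts at 9 responds at 6 or below. It is therefore plausible that the chance of response varies with the starting score. That score needs no new data: nobody enters this analysis without it. The SAP already adjusts for it when the same item is analysed as a change score, and gives no reason for dropping it when the item is dichotomised.

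Randomisation is stratified by Hurley stage and antibiotic use, not by pain, so chance imbalance in Baseline pain is not controlled by design. With 104 and 52 participants, the 95% range for a chance difference in mean Baseline pain is about ±1.96 × √(1/104 + 1/52) = ±0.33 SD.

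What is at stake is efficiency. For the single-arm dose this endpoint has the lowest power in Table 2-1: 0.53, against 0.73 for the next lowest, worst skin pain change. Section 2.4 also says the endpoint entered the testing sequence after randomisation was complete, when sample size could no longer respond. The choice of covariates could.

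**Working it through.** **1. Reproducing the stated power.** Inputs from Table 2-1 and its footnote: response 0.43 against 0.23, n = 104 and 52, two-sided 0.025 (z = 2.241).

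- Pooled proportion: (104 × 0.43 + 52 × 0.23)/156 = 56.68/156 = 0.3633.
- SE under the null: √[0.3633 × 0.6367 × (1/104 + 1/52)] = 0.0817.
- SE under the alternative: √[0.43 × 0.57/104 + 0.23 × 0.77/52] = 0.0759.
- Continuity correction: ½ × (1/104 + 1/52) = 0.0144.
- With the correction: Φ[(0.20 − 0.0144 − 2.241 × 0.0817)/0.0759] = Φ(0.03) = 0.51.
- Without it: Φ[(0.20 − 2.241 × 0.0817)/0.0759] = Φ(0.22) = 0.59.

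Exact binomial enumeration of the continuity-corrected chi-square test gives 0.526 at 0.025, 0.641 at 0.05, and 0.952 for the pooled dose (208:52, 0.53 against 0.23, at 0.025). The SAP states 0.53, 0.65 and 0.95. The SAP's figures therefore match a continuity-corrected two-proportion test. The planned analysis is a logistic Wald test, which starts higher, at about 0.59 in simulation.

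**2. Power with and without Baseline pain.** The SAP does not say how strongly Baseline pain predicts response, so this is an assumption, varied over a range. Logistic models were simulated with the overall response rates held at 0.43 and 0.23. Each trial was analysed by a Wald test with treatment alone and with treatment plus Baseline. Hurley stage, antibiotic use and analgesic use were left out of both. At 4,000 runs the simulation error is about √(0.59 × 0.41/4000) = 0.008.

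Single-arm dose, two-sided 0.025 (gains from unrounded results):

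| Log OR per SD of Baseline | AUC | Without | With | Gain (points) |
|---|---|---|---|---|
| 0 | 0.50 | 0.587 | 0.583 | −0.5 |
| 0.25 | 0.57 | 0.601 | 0.606 | +0.5 |
| 0.5 | 0.64 | 0.598 | 0.620 | +2.2 |
| 0.75 | 0.69 | 0.586 | 0.636 | +5.1 |
| 1.0 | 0.74 | 0.597 | 0.678 | +8.1 |
| 1.5 | 0.82 | 0.583 | 0.732 | +15.0 |
| 2.0 | 0.87 | 0.583 | 0.807 | +22.4 |

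At 0.05 the corresponding figures are 0.71 to 0.73 for a log OR of 0.5, 0.71 to 0.78 for 1.0, and 0.69 to 0.83 for 1.5. For the pooled dose at 0.025 they are 0.96 to 0.97 for 0.5 and 0.97 to 0.99 for 1.0.

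**3. The same check on the pain scale.** Baseline was drawn from a normal distribution (mean 5.5, SD 2, or mean 6, SD 1.8) limited to 3 to 10. Week 16 scores were limited to 0 to 10 with residual SD 2.5. All of these values are assumed; 3,000 runs each.

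- Fall unrelated to Baseline: AUC 0.50 and no gain (0.600 to 0.599; 0.569 to 0.566).
- Fall larger by 0.5 points per Baseline point: gain of about 2 points (0.595 to 0.617; 0.588 to 0.608).
- Fall larger by 0.75 points per Baseline point: gain of 5 to 6 points (0.581 to 0.637; 0.578 to 0.631).

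**4. Effect on the odds ratio.** The crude value is (0.43/0.57)/(0.23/0.77) = 2.53. Conditional on Baseline it becomes 2.65 at a log OR per SD of 0.5 and 3.01 at 1.0.

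**The case against.** The strongest reply is that nothing here is wrong. Section 4.1 makes a stated choice and Section 8.3.5.1 follows it. The models for HiSCR50, HiSCR75 and flare also carry no continuous Baseline value. The test is valid without the covariate, and the sponsor has accepted the low power in writing. All of that stands, and it is why the point is not an error. It does not amount to a reason for leaving the covariate out: accepting low power is compatible with taking an available gain. Nor is the pain model a copy of the primary one, since it already adds analgesic use.

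Four stronger readings are tempting, and the SAP does not support them.

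- A reader might infer that low Baseline scores make response impossible. Everyone analysed starts at 3 or higher, so a 3-point fall is open to all. Baseline can alter the likelihood only.
- A reader might infer that this is the weakest endpoint overall. That is true for the single-arm dose. For the pooled dose it has 0.95, and the lowest is worst skin pain change at 0.89.
- A reader might infer that a 53% step controls the passing of alpha between doses. Section 2.4 expects the pooled dose to pass alpha on, and at this step its power is 0.95. The single-arm step acts as the gate only if that dose clears all six steps at 0.025 while the pooled dose has failed one.
- A reader might set the adjusted figures against the stated 0.53 and credit the whole difference to the covariate. About 6 points of it (0.53 to 0.59) come from the continuity correction.

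**Conclusion.** The omission is real, differs from the treatment of the same item in Section 8.3.4.1, and is unexplained. Adjusting for Baseline pain costs no power beyond simulation error and gains some if Baseline predicts response. For the single-arm dose at 0.025 the gain is about 0 to 2 points for a weak link (log OR per SD up to 0.5) and 5 to 8 points for a moderate one (0.75 to 1.0). It is larger only if the link is very strong. The pooled dose gains about 1 to 2 points.

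The direction is secure. The size is not: it rests on assumed strengths of association and, in the pain-scale check, on assumed Baseline distributions, because the SAP supplies neither. This is a free improvement in efficiency and consistency. It does not affect the validity of the planned test.

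**What to change.** Before unblinding:

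- In Section 8.3.5.1, add the continuous Baseline weekly worst skin pain score, derived as in Section 8.3.4, as a covariate. Sections 8.3.5.2.1 and 8.3.5.2.2 inherit the change.
- In Section 4.1, extend the Baseline-value rule to the binary skin pain response endpoint.
- In Table 8-2, replace the cross-reference to the primary analysis for this endpoint with a statement that the odds ratio is conditional on Baseline pain as well as the other model terms, and so is not on the same basis as the HiSCR50 odds ratio.

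The cost is SAP wording and one extra model term, with no new data. The one substantive consequence is the change in what the odds ratio conditions on. The reported value may be larger than an unadjusted one even though the response rates are the same, and the text accompanying the results should say so.

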8.3.5.2.1 Nonresponse imputation

As a sensitivity analysis, any missing data at Week 16 that are not preceded by an intercurrent event (Table 8–2) will be imputed as nonresponse. That is, participants who experience an intercurrent event will be imputed as nonresponder at the timepoint of the event and all subsequent timepoints (including any recorded data after the event), and all missing data will also be imputed as nonresponse.

The same analysis model as Section 8.3.5.1 will then be used on the imputed data set.

8.3.5.2.2 Analysis on observed cases

An additional supportive analysis will be based on observed data only for study participants **with a worst skin pain score at Week 16 who have not had an intercurrent event on or before Week 16**. Study participants with missing data or who have prematurely discontinued study treatment will be treated as missing (see Section 4.2.2).

The same analysis model as in Section 8.3.5.1 will then be used on the imputed data set.

8.4 Other efficacy endpoints

The other efficacy endpoints are listed below and will be evaluated according to the planned assessments in the protocol. This excludes the timepoints for the primary and secondary endpoints specified above in Section 8.2.1 and Section 8.3.

Missing data handling for these endpoints is described in Section 4.2.1.3.

8.4.1 HiSCR endpoints

8.4.1.1 HiSCR₂₅, HiSCR₅₀, HiSCR₇₅, HiSCR₉₀, and HiSCR₁₀₀

Categorical response variables HiSCR₂₅, HiSCR₅₀, HiSCR₇₅, HiSCR₉₀, and HiSCR₁₀₀ are defined to be equal to 1 if %ΔAN is less than or equal to -25%, -50%, -75%, -90%, and -100%, respectively, and the change from Baseline in the abscess count is zero or negative (ie, non-positive) together with a non-positive change from Baseline in the draining tunnel (fistula/sinus tract) count, and 0 otherwise. This definition is introduced for identifying study participants who respond to the treatment (1 = responder, 0 = nonresponder). The definition of percentage improvement from Baseline is given in Section 8.2.1.

HiSCR₂₅, HiSCR₅₀, HiSCR₇₅, HiSCR₉₀, and HiSCR₁₀₀ response will be summarized using frequency tables by treatment group and visit.

A line plot of the HiSCR responder (HiSCR₅₀, HiSCR₇₅, HiSCR₉₀, and HiSCR₁₀₀) rate over time, by treatment group, will be produced.

In order to investigate the effect of intercurrent event handling and missing data handling on the binary response variables, the following iterations of each of the aforementioned plots (HiSCR₅₀, HiSCR₇₅, HiSCR₉₀, and HiSCR₁₀₀, respectively) will be presented, with corresponding summary statistics tables:

- Observed data only (non-imputation for either intercurrent events or missing data)

- Non-response imputation to reflect intercurrent events, non-imputation for missing data
- Full imputation: non-response imputation to reflect intercurrent events, imputation for missing data per Section 4.2.1.3

Bar charts of HiSCR₅₀, HiSCR₇₅, HiSCR₉₀, and HiSCR₁₀₀ will be produced by visit and Hurley Stage at Baseline for the Initial Treatment Period and the combined Initial and Maintenance Treatment Period. These bar charts will be repeated for HiSCR by visit and Baseline antibiotic use.

Another bar chart of HiSCR rate at Week 16 will be produced by Hurley Stage at Baseline and Baseline antibiotic use.

In addition to the above bar charts, a stacked bar chart displaying whether the criteria are met (yes/no) for each of the component data used in the calculation of HiSCR (%ΔAN, abscess count and draining tunnel [fistula/sinus tract] count) will be generated by treatment group and visit. This graph will summarize the proportion of participants in each of the 8 different yes/no binary responses at each visit (2 x 2 x 2 response combination) at each visit.

8.4.1.2 **Time to response of HiSCR₂₅, HiSCR₅₀, HiSCR₇₅, HiSCR₉₀, and HiSCR₁₀₀**

See Section 8.4.1.1 for the derivation of HiSCR.

Initial Treatment Period

Time to HiSCR₂₅, HiSCR₅₀, HiSCR₇₅, HiSCR₉₀, and HiSCR₁₀₀ (in days) during the Initial Treatment Period will each be calculated as:

Min (Date of first HiSCR_{xx} response, Date of Week 16 visit) – Date of first dose of study medication + 1, here xx represents 25, 50, 75, 90, 100 respectively. All visits including unscheduled visits are considered.

Participants who discontinue study treatment without achieving a given HiSCR response prior to Week 16 visit will be censored at the date of last lesion count assessment. Participants who reach the Week 16 Visit without achieving the given response will be censored at the date of the Week 16 Visit. Participants who experience an intercurrent event prior to achieving a HiSCR response will be censored at the date of the intercurrent event. Participants will be censored at Baseline if there is no Baseline lesion count assessment or no Post-Baseline lesion count assessment.

Time to HiSCR₂₅, HiSCR₅₀, HiSCR₇₅, HiSCR₉₀, and HiSCR₁₀₀ response during Initial Treatment Period will each be estimated and presented using the Kaplan-Meier product-limit method for each treatment group.

Kaplan-Meier plots of time to HiSCR responses will be presented by treatment group. In these Kaplan-Meier plots, the line will start at 0 (since there are no responders at Week 0) and will increase over time, representing time to achieving the response.

The median time to response, including the 2-sided 95% confidence interval, will be calculated for each treatment. Comparisons of bimekizumab vs placebo will be analyzed using a log-rank test stratified by Hurley Stage at Baseline and Baseline antibiotic use.

Combined Initial and Maintenance Treatment Period

An additional time to HiSCR₂₅, HiSCR₅₀, HiSCR₇₅, HiSCR₉₀, and HiSCR₁₀₀ (in days) during the combined Initial and Maintenance Treatment Period will be calculated as above, where the Week 48 visit is considered instead of Week 16.

Time to HiSCR₂₅, HiSCR₅₀, HiSCR₇₅, HiSCR₉₀, and HiSCR₁₀₀ response during the combined Initial and Maintenance Treatment Period will each be estimated and presented using the Kaplan-Meier product-limit method for each treatment group.

Kaplan-Meier plots of time to HiSCR responses will be presented by treatment group. In these Kaplan-Meier plots, the line will start at 0 (since there are no responders at Week 0) and will increase over time, representing time to achieving the response.

The median time to response, including the 2-sided 95% confidence interval, will be calculated for each treatment.

8.4.1.3 HiSCR₂₅, HiSCR₅₀, HiSCR₇₅, HiSCR₉₀, and HiSCR₁₀₀ response at both Weeks 16 and 48

See Section 8.4.1.1 for the derivation of HiSCR response.

The number and percentage of HiSCR₂₅, HiSCR₅₀, HiSCR₇₅, HiSCR₉₀, and HiSCR₁₀₀ responders at both Weeks 16 and 48 will be summarized based on the RS and MS.

Missing data for the above summaries will be handled using NRI. That is, participants are counted as responders only if they have an observed HiSCR at both Weeks 16 and 48 and have no intercurrent events through Week 48. Otherwise, they are treated as not responding.

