3.9 Definition of an intercurrent event

Handling of intercurrent events is one of the key elements for the analysis of efficacy endpoints.

An intercurrent event is defined as receipt of systemic antibiotic rescue medication or discontinuation of study treatment due to an AE or lack of efficacy (See Section 8.2.2).

Receipt of systemic antibiotic rescue medication is defined as initiating any systemic antibiotic on or after Baseline for any reason (including in response to an AE). The only exception to this rule is if a participant randomized to the antibiotic stratum on a tetracycline antibiotic interrupts

their stable dose of tetracycline antibiotic during the study and subsequently restarts the same tetracycline antibiotic as confirmed using the coded preferred term. The restarted dose and frequency of the antibiotic must be the same or lower than the regimen prior to the interruption.

The dates of an intercurrent event are as follows:

- For receipt of systemic antibiotic rescue medication: start date of the antibiotic
- For discontinuation of study treatment due to an AE or lack of efficacy: Last study treatment date + 17 days. Note: study treatment discontinuation includes study discontinuation.

The choice of 17 days is intended to capture the interval between dosing and lesion assessments (14 days), as well as the visit window (3 days).

An additional sensitivity analysis will be conducted where missing data due to COVID-19 will be considered an intercurrent event and will be imputed as a nonresponse at that particular visit. This will be identified when there are missing data at a visit that has been impacted by COVID-19 according to the COVID-19 impact CRF page. The date of this intercurrent event will be the date of the impacted visit.

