4.2.1.1 Handling missing data for the primary efficacy endpoint

If study participants have an intercurrent event as defined in Section 3.9, then the primary efficacy variable at that timepoint and all subsequent timepoints (whether the data were observed or not) will be set to “nonresponse” as the study participant has not met the criteria for response based on the composite estimand defined in Section 8.2. All remaining missing data for the endpoint will be imputed using multiple imputation Markov-Chain Monte Carlo method (MI-MCMC)/monotone regression for the primary analysis.

In addition, sensitivity analyses using NRI, MI-MCMC/reference-based methods, tipping point analysis, and observed case (OC) methods will be performed, which will assess the impact of different methods of handling missing data.

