8.2 Primary efficacy endpoint

The primary and sensitivity analyses of HiSCR₅₀ response at Week 16 are summarized in Table 8–1.

Table 8–1: Estimand Details and Attributes for Primary Endpoint

Objective Clinical Category	Statistical Category (Section)	Estimands for Primary Endpoint			PLS (Analysis)
		Variable/Endpoint	Pop	IES	
Primary Objective: To evaluate the efficacy of bimekizumab in study participants with moderate to severe HS					
HiSCR ₅₀	Primary (Section 8.2.2)	HiSCR ₅₀ response at Week 16	RS	The main intercurrent events are receipt of systemic antibiotic rescue medication or discontinuation of study treatment due to an AE or lack of efficacy prior to Week 16. A composite strategy will be used, ie, the occurrence of an intercurrent event will be handled by evaluating the corresponding participants as treatment failures (nonresponders).	The odds ratio versus placebo based on a logistic regression. Missing values will be imputed using MI – MCMC/Monotone Regression under a missing at random assumption.

Table 8–1: Estimand Details and Attributes for Primary Endpoint

Objective Clinical Category	Statistical Category (Section)	Estimands for Primary Endpoint			PLS (Analysis)
		Variable/Endpoint	Pop	IES	
HiSCR ₅₀	Sensitivity (Section 8.2.3.1)	HiSCR ₅₀ response at Week 16	RS	Composite strategy , as for the primary analysis where the occurrence of an intercurrent event will be handled by evaluating the corresponding participants as nonresponders.	The odds ratio versus placebo based on a logistic regression. Missing values for any other reason will also be imputed as nonresponders.
HiSCR ₅₀	Sensitivity (Section 8.2.3.2)	HiSCR ₅₀ response at Week 16	RS	Composite strategy , as for the primary analysis.	The odds ratio versus placebo based on a logistic regression. Missing values will be imputed using MI – Reference-Based Regression under a missing not at random assumption.

Table 8–1: Estimand Details and Attributes for Primary Endpoint

Objective Clinical Category	Statistical Category (Section)	Estimands for Primary Endpoint			PLS (Analysis)
		Variable/Endpoint	Pop	IES	

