8.4.1.4 HiSCR₅₀, HiSCR₇₅, HiSCR₉₀, and HiSCR₁₀₀ among Week 16 Responders

See Section 8.4.1.1 for the derivation of HiSCR response.

Summaries of HiSCR₅₀, HiSCR₇₅, HiSCR₉₀, and HiSCR₁₀₀ responders at each visit from Week 16 through Week 48 will be summarized based on a subset of participants in the MS who achieve response at Week 16. The summaries will be as follows:

- HiSCR₅₀ responder rate based on participants who achieved HiSCR₅₀ response at Week 16
- HiSCR₇₅ responder rate based on participants who achieved HiSCR₇₅ response at Week 16
- HiSCR₉₀ responder rate based on participants who achieved HiSCR₉₀ response at Week 16
- HiSCR₁₀₀ responder rate based on participants who achieved HiSCR₁₀₀ response at Week 16

Line plots of the above HiSCR responder rate categories over time (from Week 16 to Week 48), by treatment group, will be produced.

8.4.1.5 Time to loss of response of HiSCR₅₀, HiSCR₇₅, HiSCR₉₀, and HiSCR₁₀₀ in Week 16 responders

See Section 8.4.1.1 for the derivation of HiSCR response.

Time to loss of response will be based on the MS and include only participants who had the corresponding HiSCR response at Week 16 (considering intercurrent event handling from the composite estimand described in Section 8.2.2).

Time to loss of response of HiSCR₅₀, HiSCR₇₅, HiSCR₉₀, and HiSCR₁₀₀ (in days) is defined as: Date of loss of response of HiSCR₅₀, HiSCR₇₅, HiSCR₉₀, and HiSCR₁₀₀ - Date of Week 16 treatment administration + 1.

Time to loss of response will be estimated and presented using the Kaplan-Meier product-limit method for each treatment. Participants who experience an intercurrent event prior to loss of response will be considered as having lost response on the date of intercurrent event. Participants who reach the Week 48 Visit without loss of response will be censored at the date of the Week 48 Visit. Participants who discontinue treatment or study, for reasons other than those already defined for an intercurrent event, and who have not yet displayed loss of response by the time of withdrawal, will be censored at the date of the last lesion count assessment.

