8.4.3 Flare relative to Baseline

See Section 8.3.2 for the derivation of flare.

Disease flare status will be summarized by treatment group and visit using frequencies and percentages. The denominator for the percentage calculations will be the number of participants with non-missing data in each treatment group. This summary will also include the number of participants with any flare in the Initial Period, Maintenance Period, and the combined Initial and Maintenance Period. A bar chart of percentage of participants with flare, by visit and treatment, will be presented.

In addition, for each participant, the number of flares during the Initial Treatment Period will be calculated and summarized by treatment group. A corresponding histogram summarizing the number of flares during the Initial Treatment Period will be presented.

8.4.4 Time to flare by Week 16

See Section 8.3.2 for the derivation of flare.

Time to flare (in days) during the Initial Treatment Period will each be calculated as:

Min (Date of first flare, Date of Week 16 visit) – Date of first dose of study medication + 1.
All visits in the Initial Treatment Period including unscheduled visits are considered.

Participants who discontinue study treatment without experiencing a flare prior to Week 16 Visit will be censored at the date of last lesion count assessment. Participants who reach the Week 16 Visit without experiencing a flare will be censored at the date of the Week 16 Visit. Participants who experience an intercurrent event prior to experiencing a flare will be treated as experiencing a flare at the date of the intercurrent event. Participants will be censored at Baseline if there is no Baseline lesion count assessment or no Post-Baseline lesion count assessment.

Time to flare will be estimated and presented using the Kaplan-Meier product-limit method for each treatment group.

Kaplan-Meier plots of time to flare will be presented by treatment group. In these Kaplan-Meier plots, the line will start at 0 and will increase over time, representing time to achieving the response.

The median time to flare, including the 2-sided 95% confidence interval, will be calculated for each treatment. Comparisons of bimekizumab vs placebo will be analyzed using a log-rank test stratified by Hurley Stage at Baseline and Baseline antibiotic use.

8.4.5 Time to flare by Week 48

See Section 8.3.2 for the derivation of flare relative to Baseline.

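### Time to HiSCR response censors participants at an intercurrent event that the SAP elsewhere scores as nonresponse or failure, which raises each response curve

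*SAP*

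**What the plan says.** **The rule.** SAP Section 8.4.1.2 (time to response of HiSCR25 to HiSCR100): "Participants who experience an intercurrent event prior to achieving a HiSCR response will be censored at the date of the intercurrent event". The times "will each be estimated and presented using the Kaplan-Meier product-limit method for each treatment group", with medians. For the Initial Treatment Period, "Comparisons of bimekizumab vs placebo will be analyzed using a log-rank test stratified by Hurley Stage at Baseline and Baseline antibiotic use". The analysis to Week 48 uses the same calculation with the later visit, so the rule carries over.

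**The event.** Section 3.9 names two kinds: starting a systemic antibiotic as rescue, and stopping study treatment because of an adverse event or for want of efficacy.

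**The same participants in the HiSCR binary analyses.**
- Sections 4.2.1 and 4.2.1.1 require freedom from these events for a positive outcome. They set nonresponse at the event and at every later timepoint, "as the study participant has not met the criteria for response based on the composite estimand defined in Section 8.2".
- Section 4.2.1.3 and Table 4-1 carry the primary method to other responder endpoints.
- The fully imputed HiSCR displays in Section 8.4.1.1 score the event as nonresponse. So does HiSCR at both Weeks 16 and 48 (Section 8.4.1.3).

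**The same participants in related time-to-event analyses.**
- Time to loss of response (Section 8.4.1.5): they "will be considered as having lost response on the date of intercurrent event".
- Time to flare (Sections 8.4.4 and 8.4.5): they "will be treated as experiencing a flare at the date of the intercurrent event".

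**The concern.** Censoring in Kaplan-Meier says that a participant's later chance of response is that of the people still under observation. That is hard to accept for someone who has stopped for lack of efficacy, or who needed rescue antibiotics before responding. In the plan's own HiSCR analyses such a person can no longer become a responder.

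Two things follow. First, the curve no longer estimates the proportion who respond before any intercurrent event; it ends above it. Second, it is not a clean estimate of response had no event occurred either, because leaving the risk set is related to outcome. At stake are the response curves, their medians and the stratified log-rank comparison in 8.4.1.2.

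**Working it through.** **1. Inputs.** Table 2-1 gives HiSCR50 rates of 0.25 (placebo, N=70), 0.50 (bimekizumab, N=140) and 0.60 (pooled bimekizumab, N=280). They are Week 16 rates; I use them as the cumulative proportion responding by Week 16. The SAP gives no intercurrent-event rate, so 5% to 30% is assumed.

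**2. The plan's own figure.** No stated figure is in dispute, but the inputs can be checked against the power for 0.50 vs 0.25 at two-sided 0.025, 140 vs 70.
- Pooled proportion = (70×0.25 + 140×0.50)/210 = 0.4167; null SE = √(0.4167×0.5833×(1/70+1/140)) = 0.0722.
- Alternative SE = √(0.1875/70 + 0.25/140) = 0.0668.
- Power = Φ((0.25 − 2.241×0.0722)/0.0668) = 0.907, against 0.90 stated. For 0.60 vs 0.25 the same method gives 0.9996, against 0.99 stated.

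**3. Formula.** Let R be the proportion responding and I the proportion with an intercurrent event before response. With constant cause-specific hazards over 16 weeks, the total cumulative hazard is L = −ln(1 − R − I). With the event censored, Kaplan-Meier ends at K = 1 − exp(−L·R/(R+I)). The proportion responding before any event is R.

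Example, placebo with I = 20%: L = −ln(0.55) = 0.5978; 0.5978 × 0.25/0.45 = 0.3321; K = 1 − exp(−0.3321) = 28.3%, against 25.0%.

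**4. Week 16 curve under the written rule.**

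| R | I = 5% | I = 10% | I = 20% | I = 30% |
|---|---|---|---|---|
| 25% | 25.7% | 26.5% | 28.3% | 30.4% |
| 50% | 51.6% | 53.4% | not run | not run |
| 60% | 62.1% | 64.4% | not run | not run |

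The excess over R runs from 0.7 to 5.4 points.

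**5. Timing matters.** If 14 of 70 placebo participants (20%) had the event before any of 17 responses, Kaplan-Meier gives 17/56 = 30.4% against 17/70 = 24.3%. That is 6.1 points, against 3.3 points for 20% events in the table.

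**6. Medians.** For R = 50%, the proportion responding before any event reaches 50% at Week 16. Under censoring the 16-week response hazard is 0.7259 (I = 5%) or 0.7636 (I = 10%). The median is then 16×0.6931/0.7259 = 15.3 weeks or 16×0.6931/0.7636 = 14.5 weeks. The placebo curve stays below 50% under either rule, so its median is not reached.

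**7. Contrast, 50% vs 25%.** With events counted as nonresponse the difference is 25.0 points and the hazard ratio ln(0.50)/ln(0.75) = 2.41. Under censoring (unrounded values carried through):

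| Events, placebo / active | Difference | Hazard ratio |
|---|---|---|
| 5% / 5% | 25.9 points | 2.44 |
| 20% / 10% | 25.1 points | 2.30 |
| 20% / 5% | 23.4 points | 2.19 |

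**8. Overlapping dates.** Section 8.4.1.2 also censors anyone who stops treatment without response at the last lesion count. A participant who stops for an adverse event or lack of efficacy therefore has two censoring dates: that one, and the event date of last dose plus 17 days (Section 3.9). No precedence is given. Section 8.4.1.5 avoids this by limiting its discontinuation rule to reasons that are not intercurrent events.

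**The case against.** The strongest defence is that no stated rule is broken. Section 4.2.3 assigns the composite strategy to the primary and binary secondary endpoints, Section 4.2.1.3 extends the primary method to other binary endpoints, and nothing assigns it to time to response. The plan also uses a hypothetical strategy for continuous endpoints, and censoring at the event is its time-to-event counterpart. This stands: a reader might infer a breach of the composite strategy, but the documents show an unexplained change of approach for the same response concept.

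Flare and loss of response are unfavourable events, so their rule cannot be copied directly. That is also right. The counterpart for a favourable event is to remain a nonresponder. Nor is 8.4.1.2 the only place that censors at such an event: time to rescue therapy (Section 8.4.10) censors study discontinuation for any reason.

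The practical weight is limited. The endpoint is outside the sequence in Section 4.5 and is not among the nominal tests in Section 8.5. Two of the three HiSCR display versions in Section 8.4.1.1 score the event as nonresponse, and Section 8.4.11 shows time to intercurrent event by arm. This lowers the severity, but it does not supply a reason for the rule.

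**Conclusion.** The point holds as an unexplained and outcome-related censoring rule that biases each response curve upward relative to the proportion responding before any intercurrent event, and makes medians early where they are reached. The size is about 1 to 5 points per arm at Week 16. This rests on Table 2-1 rates read as cumulative response, constant hazards, and assumed event rates of 5% to 30%; earlier events would give more.

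Three stronger readings are not supported:
- That these participants are treated as future responders. They are given the same chance as those still at risk, not a certain response.
- That placebo is overstated most, or that the comparison is biased in a known direction. The SAP gives no event rates. At equal 10% rates the 50% arm rises by 3.4 points and placebo by 1.5, and the contrast can move either way.
- That the rule explains any gap from the Week 16 HiSCR rates. Section 8.4.1.2 counts first response at any visit, including unscheduled ones, while the primary endpoint is status at Week 16. The two would differ in any case; censoring adds an avoidable part.

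The primary result and type I error control are unaffected. The change is advisable rather than essential.

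**What to change.** In Section 8.4.1.2:

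1. Keep a participant with an intercurrent event before response in the risk set as a nonresponder. Censor at the Week 16 visit date (Week 48 for the combined period), or at the planned date if there is no such visit. With no other censoring before then, the curve ends at R. Alternatively, report cumulative incidence with the intercurrent event as a competing event.
2. Restrict the sentence that censors treatment discontinuers at the last lesion count to discontinuations for reasons other than an intercurrent event, as Section 8.4.1.5 already does.
3. Keep the present censoring rule, if wanted, only as a labelled sensitivity display.

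The cost is two edited sentences, a planned-date rule and a revised censoring variable. With the first option the planned estimator and stratified log-rank test can stay. No new data are needed.
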